#### Minimal necessary sample size to fit the multivariable models

For the binary outcome of guideline-concordant care, the model for sensitivity analyses will have up to 9 degrees of freedom (intercept + 3 (4 sites) + 4 (five time periods) + 1 for treatment). Using the rule of tens, we must have at least 90 outcomes. In the worst case scenario, there will be no treatment effect and 25% of the sample should have the outcome. This yields a minimal needed sample of  $90/0.25 = 360$ . In a univariable test, assuming a minimal detectable difference of 0.25, The power attainable would be 99.9%.

In the event that the treatment and control groups are imbalanced for some covariates, and 5 parameters are added, approximately 140 outcomes will be necessary to fit the model adequately. Then the minimal sample size becomes:  $140/0.25 = 560$ . In a univariable test, assuming a minimal detectable difference of 0.25, The power attainable would be >99.9% under the expected sample size of 2054.

### **3. Aims and objectives**

The objective of this trial is to test whether implementing a CDS tool for prediction of septic shock in four Emergency Departments within the Children's Hospital Colorado network increases the proportion of children with suspected sepsis who receive guideline-concordant septic shock care, decreases the time to antibiotics, decreases the proportion of patients with septic shock, decreases the proportion of patients who experience mortality within 30 days of hospital arrival. An additional objective is to assess the balancing measure of whether the proportion of patients with suspected sepsis who receive intravenous antibiotics increases.

### **4. Outcomes**

#### 4.1 Primary outcome

##### Number of Patients Receiving Guideline-Concordant Septic Shock Care

Treatment will be defined as concordant with Surviving Sepsis Campaign guidelines for shock if intravenous antibiotics are initiated within 60 minutes of sepsis recognition and an intravenous fluid bolus is initiated within 60 minutes of sepsis recognition. This will be a binary outcome. Sepsis recognition is defined as the earlier of: sepsis page sent, sepsis orderset use, or intravenous antibiotic order.

[Time Frame: Up to 24 hours after Emergency Department arrival]

#### 4.2 Secondary outcomes

##### Time to Antibiotics

Time to antibiotics will be measured in minutes from the time of sepsis recognition to the start of intravenous antibiotic treatment. This will be a time-to-event outcome. Sepsis recognition is defined as the earlier of: sepsis page sent, sepsis orderset use, or intravenous antibiotic order.

[Time Frame: Up to 24 hours after Emergency Department arrival]

##### Number of Patients With Septic Shock

Septic shock will be defined as suspected infection and systolic hypotension and either vasoactive use or  $\geq 30$  ml/kg intravenous bolus fluid administration

[Time Frame: Up to 24 hours after Emergency Department arrival]

##### 30-Day In-Hospital Mortality

The number of patients who experience an in-hospital death up to 30 days after Emergency Department arrival.

[Time Frame: 30 days after Emergency Department arrival]

##### Number of Patients Receiving Intravenous Antibiotics during Emergency Department care

[Time Frame: Up to 24 hours after Emergency Department arrival]

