## 1. Introduction

Septic shock is a leading global cause of pediatric death. In the US, the in-hospital mortality rate for children with sepsis is 5-20%. Septic shock is a state of critical infection that requires advanced and resource-intensive resuscitation, and morbidity-free survival depends on timely diagnosis. Critical care delivered in a delayed fashion, after a child is in hypotensive shock, is less effective; for each hour of unrecognized shock the odds of death more than double. Advances have been made in timely sepsis treatment, but improving diagnosis of septic shock in children remains elusive. Improved early diagnosis would accelerate treatment and improve outcomes.

Tools that have been deployed to improve diagnosis in pediatric sepsis either diagnose it after organ dysfunction criteria have been met, or depend heavily on subspecialty physician judgment and have not been tested outside of tertiary pediatric hospitals. Thus, the evidence-based 2020 Surviving Sepsis Children's Guidelines for pediatric sepsis stated that "high-quality trials on pediatric sepsis recognition are lacking, and data are not sufficient to suggest any particular screening tool," and identified pediatric sepsis recognition trials as an important research need. Despite this, the guidelines weakly recommended screening patients "who present as acutely unwell" for septic shock, citing very low quality evidence. The guidelines also stated that there is no evidence for the effectiveness of any existing pediatric sepsis screening tools.

This study addresses a gap in knowledge about the effectiveness of pediatric sepsis prediction tools. The study team has developed and retrospectively validated early diagnostic models that leverage clinical data in the Electronic Health Record (EHR) to predict septic shock in children in the emergency setting. In order to address concerns about alert fatigue and antibiotic overuse, these predictive models were designed to identify patients at high risk for shock among patients in whom clinicians initially had some suspicion for sepsis.

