### 2.1 Sample size calculation

The unit of analysis for this study is ED patients with suspected sepsis. The necessary enrollment size was used to calculate the study period necessary to achieve power, based on historic volume trends. The main calculations were done using the `pwr` package for R.

During the study period, we expect 2054 patients to be identified and exposed to decision support (CDS). With current care patterns, we would expect 25% (514) to receive guideline-

concordant septic shock care prior to shock occurring. In the literature, use of pediatric sepsis quality interventions has increased rates of concordant early care of shock to 50% (1027). With an estimated effect of the alert of increasing rates of concordant care from 25% to 50%, using a significance of 0.05, we anticipate >90% power to detect this difference. We will have 80% power to detect an increase of 6%.

For the outcome of time to receipt of antibiotic, we expect that 79% of patients will receive antibiotics. Among those who do receive antibiotics, with current care patterns, in pilot data we have observed a mean time to antibiotics of 55 minutes, or a mean log time of 4.0 (SD 1.29). In published pediatric sepsis literature, the use of pediatric sepsis quality interventions has decreased the log time to antibiotic to 3.3 (SD 1.54). Using a significance of 0.05, we anticipate >90% power to detect a difference in this outcome. We have 80% power to detect a smaller difference of 4.0 vs 3.8 (55 to 45 minutes). Even under conditions of very slow accrual where half of the hypothesised sample is realized, we would have 80% power to detect a difference of 4.0 vs 3.72 (55 to 41 minutes).

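### The antibiotic balancing outcome counts only ED antibiotics, which is narrower than its objective, so earlier treatment of the same children can appear as more treatment

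*SAP*

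**What the plan says.** SAP section 3 names one balancing measure: "whether the proportion of patients with suspected sepsis who receive intravenous antibiotics increases". It sets no limit of place or time.

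Section 4.2 lists the matching outcome as "Number of Patients Receiving Intravenous Antibiotics during Emergency Department care", with the time frame "Up to 24 hours after Emergency Department arrival". It does not say how to count a child who leaves the ED untreated and gets a first IV dose elsewhere before 24 hours.

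Three other places bear on this:

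- Section 1 says that concern about overuse shaped the models ("In order to address concerns about alert fatigue and antibiotic overuse").
- Section 3 gives an intended effect of the tool: that it "decreases the time to antibiotics".
- Section 2.1 states "we expect that 79% of patients will receive antibiotics", without saying whether this is an ED share or a 24-hour share.

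**The concern.** A balancing measure should stay still when the intervention does only what it is meant to do, and move when the unwanted effect occurs. Here the wanted effect is earlier antibiotics and the unwanted effect is antibiotics for more children. A count that stops at the ED door does not separate them. Suppose a child would have had a first dose on the ward at hour six and, with the tool, has it in the ED at hour two. That child is a no under control and a yes under intervention, yet would have been treated either way.

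The ED count also depends on how long children stay in the ED. A longer stay brings more first doses inside the count and a shorter stay pushes them out, whatever happens to total use.

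At stake is how the trial's one named balancing measure is read. A rise could be taken as overuse when it is a change in timing. If ED stay shortened, a real rise could be partly hidden.

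**Working it through.** **Reading the passages together.** The objective covers all IV antibiotic use in children with suspected sepsis. The outcome covers use in the ED. The difference between them is first doses given after leaving the ED and within 24 hours of arrival. No defined outcome in the SAP recovers those doses: the time-to-antibiotic analysis in section 6.2 censors at ED discharge, and arrival to antibiotic administration is listed in section 4.2 without a definition or window.

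**Inputs from the SAP.**

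- Total sample 2054 and 79% receiving antibiotics (section 2.1).
- Two-sided 5% level (section 6).
- The SAP sets no power, margin or threshold for this outcome, so there is no figure of its own to reproduce.

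**Assumptions.**

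- Equal arms: 2054 / 2 = 1027. The SAP gives no split. Its four sites and five periods give 0 + 1 + 2 + 3 + 4 = 10 intervention site-periods out of 20, so an even split is a reasonable starting point if volumes are similar.
- s = share of all children who, under control, start IV antibiotics after the ED but within 24 hours. Not in the SAP; range 4% to 8%.
- m = share of those whose first dose the tool moves into the ED. Not in the SAP; taken as one half.
- The same children are treated by 24 hours in both arms. ED stay is unchanged. Clustering and time effects are ignored.

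**Size of the artefact.** The spurious rise in the ED count is s × m.

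- s = 0: 0 points.
- s = 4%: 0.04 × 0.5 = 0.02, or 2 points.
- s = 8%: 0.08 × 0.5 = 0.04, or 4 points.

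Under a 24-hour, any-location count the difference is 0 in every case, because the same children are counted in both arms.

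**Detectable difference.** With the arcsine effect size h = 2·asin(√p₂) − 2·asin(√p₁), 80% power needs h = (1.960 + 0.842) / √(1027/2) = 2.802 / 22.66 = 0.1236. From p₁ = 0.79, 2·asin(√0.79) = 2.1895. Adding 0.1236 gives 2.3131, so p₂ = sin²(2.3131/2) = 0.838. The detectable rise is about 4.8 points.

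**Chance that a pure timing shift gives a significant rise**, Φ(h × 22.66 − 1.960):

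| What 79% means | ED share, control to intervention | h | Chance |
|---|---|---|---|
| ED share | 79% to 81% | 0.0500 | about 20% |
| ED share | 79% to 83% | 0.1021 | about 64% |
| 24-hour share, s = 4% | 75% to 77% | 0.0468 | about 18% |
| 24-hour share, s = 8% | 71% to 75% | 0.0902 | about 53% |

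With s = 0 the chance is the nominal 2.5% in that direction. Allowing for clustering would generally lower the other chances; it would not change the size of the artefact.

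**The case against.** The strongest reply is that ED scope is deliberate. The tool goes to ED providers, so an ED count measures the behaviour it acts on, while a 24-hour count adds inpatient decisions that it does not target. The label and the time frame can be read together, as ED doses with 24 hours as an outer limit. The same frame follows the primary outcome, time to antibiotics and septic shock, so it looks like a standard bound. Section 3 is a summary, and section 4.2 makes it operational.

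Much of this stands. A reader might infer that the label and the frame contradict each other outright; the joint reading shows that they need not. But that reading settles on the ED-only count, which is the count that mixes timing with use, and leaves the outcome narrower than the objective. The point about inpatient decisions is a fair cost of the wider count and a reason to keep the ED count alongside.

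A reader might also infer that the outcome will show a false rise. The SAP does not support that. It gives neither the share first treated after the ED nor any share that the tool would move, and a shorter ED stay could push the count down. Nor does the SAP attach a threshold or action to this measure. Finally, the listed arrival-to-administration time and ED disposition may help an analyst to see a timing shift, although neither is defined for that purpose.

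**Conclusion.** The point holds as a mismatch between objective and outcome that can bias the balancing measure. It is minor. The ED-only count can record earlier treatment of the same children as an increase, and it moves with ED length of stay in either direction.

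The size cannot be derived from the SAP. It is zero if no first doses fall after the ED, and 2 to 4 points under the assumed 4% to 8% with half moved. Those values lie below the 4.8 points detectable with 80% power, but they are not negligible: under the same simple assumptions they would give a significant rise about 18% to 64% of the time. All of this rests on assumed shares, 1027 per arm and no allowance for clustering. It shows what could happen and does not forecast what will.

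**What to change.** Define the balancing measure in section 4.2 as the proportion of children with suspected sepsis who start any IV antibiotic within 24 hours of ED arrival, in any location. Report the ED-only proportion beside it. If the ED count rises and the 24-hour count does not, the change is one of timing or place; if both rise, more children are being treated. State also whether the 79% in section 2.1 is an ED share or a 24-hour share.

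The cost is mainly SAP wording, because the 24-hour window is already stated for this outcome. The small downside is that the 24-hour count includes some inpatient decisions outside the tool's reach, and the paired ED count keeps that visible. The change concerns measurement only and no treatment rule.

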##### Other hospital course and resource utilization outcomes

Organ dysfunction laboratories measured

Sepsis orderset used

Arrival to Antibiotic Administration

ED Disposition

24-Hour hypotension

Intravenous crystalloid fluid volume administered/kg in the first 24 hours

Vasoactive agent used during hospitalization

Positive pressure ventilation during hospitalization

Hospital Length of Stay

ICU within 24 hours

ICU Length of Stay

Proportion of all ED patients triggering the CDS

#### 4.3 **Safety outcomes**

Adverse events will be identified upon occurrence and on data review at the DSMC interim safety review and end of the study period.

## 5. Populations and subgroups to be analyzed

### 5.1 Subgroups

The primary analysis will be conducted in all patients meeting inclusion criteria. A subgroup analysis for the same outcomes will be conducted only in the subgroup of patients identified as high-risk by either the arrival or two-hour models. Assuming sufficient sample size, we will perform subgroup analyses in race/ethnicity groups, to assess whether the intervention differentially impacts socially constructed subgroups.

## 6. Analyses

The primary hypothesis will test whether the proportion of patients receiving guideline-concordant septic shock care is greater in the intervention arm compared to the control arm. An odds ratio will be calculated to assess this, and will be considered significant if the 95% confidence interval does not contain 1.0.

Analyses will be conducted at the level of the patient encounter using the generalized linear model framework. The primary analysis will include an effect for intervention, and subsequent sensitivity analyses will include fixed effects for time and site to test for heterogeneity of effect. Up to five additional covariates will be included if they are imbalanced between the two arms of the trial. We will construct tables comparing the medians and proportions of clinically meaningful variables that might be expected to affect the association between the intervention and the outcome of guideline-concordant care. These potential covariates considered will include patient characteristics, provider type, arrival modality, triage level, and social determinants of health, including race, ethnicity, and insurance status. Standardized differences will be used to assess the magnitude of difference in covariates between arms. Anywhere that we find significant imbalance between arms, that variable will be included as a covariate.

Significance of effects will be assessed at the 5% level, with all tests structured as two sided hypotheses. SAS software version 9.4 (SAS Institute, Cary, NC) and R version 4 (R Foundation for Statistical Computing, Vienna, Austria) will be used for all data management and statistical analysis.

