## 2. Study design

This study is a prospective, stepped-wedge cluster randomized trial to test the effectiveness of implementing a Clinical Decision Support (CDS) tool for prediction of septic shock in four Emergency Departments (ED) within a pediatric healthcare network. The site will be the unit of randomization. All ED providers at the site will receive the CDS intervention when their site receives the intervention. The outcomes will be measured at the patient level. There will be five, 10-week study periods and four sites. In the first period, no sites will receive the intervention. During each subsequent period, one site will crossover to receive the intervention.

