### 6.2 Secondary outcomes (continuous – time to antibiotic)

The secondary hypothesis will test whether the time to antibiotics is shorter in the intervention arm compared to the control arm. A hazard ratio will be calculated to assess this, and considered significant if the 95% confidence interval does not contain 1.0. The following approach will be used.

Time will be measured beginning with admission to the ED and concluding with administration of antibiotics (an event) or discharge from the ED (censoring). Death is expected to be rare and will be treated as a censoring event. Analysis will use a Cox proportional hazard model with a fixed binary effect for treatment.

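### Sites are randomised, but no model allows for correlation within a site or site-period: the primary CI is too narrow if sites differ, and adding site and period cures this only if sites do not drift apart

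*SAP*

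**What the plan says.** Section 2 describes the design: "This study is a prospective, stepped-wedge cluster randomized trial to test the effectiveness of implementing a Clinical Decision Support (CDS) tool". It adds "The site will be the unit of randomization", "There will be five, 10-week study periods and four sites" and "During each subsequent period, one site will crossover to receive the intervention". No site has the tool in the first period.

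Section 6 fixes the analysis: "Analyses will be conducted at the level of the patient encounter using the generalized linear model framework". The primary model has an intervention effect only; fixed time and site effects enter in later sensitivity analyses. Section 2.1, on the minimum sample for the multivariable models, lists that larger model's parameters: "the model for sensitivity analyses will have up to 9 degrees of freedom (intercept + 3 (4 sites) + 4 (five time periods) + 1 for treatment". Section 6.2 says of time to antibiotics: "Analysis will use a Cox proportional hazard model with a fixed binary effect for treatment".

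The odds ratio and the hazard ratio are each called significant if the 95% CI excludes 1.0, at a two-sided 5% level. Nowhere does the SAP name a random effect, frailty, GEE, cluster-robust variance, ICC or design effect.

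**The concern.** Treatment switches by whole site-period, so anything that moves a whole site or a whole site-period moves the treatment contrast. A standard error that counts each encounter as independent leaves this variation out.

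Two kinds of variation matter. Stable differences between sites, and trends shared by all sites, are missed by the primary model but removed by fixed site and period terms. A site's own drift from one 10-week period to the next (staffing, local initiatives, case mix) is in no model in the SAP.

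The decision rule is the CI. If it is too short, the stated 5% level is not the real one for the primary outcome. The same mechanism applies to the Cox model.

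**Working it through.** **Inputs from the SAP.** 4 sites x 5 periods = 20 cells, 10 control and 10 intervention (section 2). Section 2.1 says "we expect 2054 patients to be identified and exposed to decision support (CDS". I read 2054 as the whole-trial total, which gives 2054/20 = 102.7, about 103 per cell. The control rate is 25%.

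**Assumptions, because the SAP gives no values.** Equal cells, no secular trend unless stated, ICC on the proportion scale, and CAC = the share of between-cluster variance that is constant over time. An ICC of 0.01 is a between-cell SD of sqrt(0.01 x 0.25 x 0.75) = 4.3 points; 0.02 is 6.1 points.

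**The plan's own figures.** With two independent arms of 1027, 25% v 50% has power above 99.9%. The difference detectable with 80% power is 5.5 points (6 when rounded; power at exactly 31% is 85.8%). The stated figures thus reproduce as independent-patient calculations with no design effect.

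**Primary model (intervention only).** Between-cluster variance enters the contrast of 10 v 10 cells with these weights:
- Site-period variation: 20 x (1/10)² = 0.20.
- Stable site variation: the sites' net weights are 0.3, 0.1, -0.1 and -0.3, so the sum of squares is also 0.20.

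The inflation therefore depends on the ICC and not on the CAC. Variance factor = 1 + 102 x ICC; type I error = 2 x [1 - Φ(1.96/√factor)].
- ICC 0.01: factor 2.02, √ = 1.42, type I error 17%.
- ICC 0.02: factor 3.04, √ = 1.74, type I error 26%.

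Simulated null trials gave about 16-17% and 25-26%.

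**Site + period model (9 parameters).** Only the drifting share remains, so factor = 1 + 102 x ICC x (1 - CAC), with the same type I formula.

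| ICC | CAC | factor | formula | simulation |
|---|---|---|---|---|
| 0.01 | 0 | 2.02 | 17% | about 16% |
| 0.01 | 0.5 | 1.51 | 11% | about 11% |
| 0.01 | 0.8 | 1.20 | 7% | about 8% |
| 0.01 | 1 | 1.00 | 5% | about 5% |
| 0.02 | 0 | 3.04 | 26% | about 27% |
| 0.02 | 0.5 | 2.02 | 17% | about 17% |
| 0.02 | 0.8 | 1.41 | 10% | about 11% |
| 0.02 | 1 | 1.00 | 5% | 4-5% |

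At ICC 0.01 and CAC 0, the model SE of the log OR is 0.187 against a true SD of 0.264. The ratio is 0.71, so the CI is about 30% too short.

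**Shared trend.** Intervention cells lie on average two periods later than control cells. A trend of 0.1 log-odds per period therefore biases the intervention-only log OR by 2 x 0.1 = 0.20. With no clustering, that model then rejects a true null in about 55% of simulated trials; the site + period model rejects in 5-6%.

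**A cell-level check.** An unweighted regression of the 20 empirical log odds on intervention, site and period, with 11 residual df, rejected in about 4-6% of null trials in every setting run.

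**The case against.** The strongest reply is that the site-and-period model already deals with clustering. In part this stands. If site differences are constant over the 50 weeks, fixed site terms remove them and the test holds its level (4-6%) at every ICC tried. A reader might infer that the adjusted CIs are too narrow in any case. The SAP does not support that: it gives no site-by-period variance, so the defect in that model is conditional. The 16% and 27% at CAC 0 are the top of the range for their ICC. Nor does it follow that adjusting for site and period gains nothing. At ICC 0.02 and CAC 0.8 it lowers the error from about 25% to about 11%, and it removes the bias from a shared trend.

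This reply does not rescue the primary result, because the deciding CI comes from the intervention-only model.

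It could also be said that a generalized linear model framework might be stretched to include mixed models or GEE. The text points the other way: section 6 names fixed effects, section 2.1 counts 9 parameters with none for site-by-period, and section 6.2 names a single fixed treatment effect. The variance model belongs in the SAP, so the unseen protocol does not settle the matter.

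Finally, one might infer that the trial cannot show its planned effect once clustering is respected. The calculations do not support that (see the fix).

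**Conclusion.** The concern holds in conditional form.
- **Primary CI:** too narrow if sites differ, whether stably or by period. Real type I error is about 16-17% at ICC 0.01 and 25-26% at ICC 0.02, against a nominal 5%. A shared time trend would also bias the estimate.
- **Site + period CI:** too narrow only if sites drift differently between periods. The error runs from about 5% (CAC 1) to about 16% (CAC 0) at ICC 0.01, and from about 5% to about 27% at ICC 0.02.
- **Time to antibiotics:** the model has the same omission and the same direction is expected, but no figure was computed.

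The sizes rest on assumed ICC and CAC values, equal cells of 103 and a 25% base rate. The omission itself rests on the SAP's text alone. Since the primary significance claim depends on this CI, it should be settled before analysis.

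**What to change.** **Section 6.** Make the primary model logistic with intervention, fixed site, fixed period and a random site-by-period intercept (20 cells). Take the CI from a t reference with 20 - 9 = 11 df. An alternative is a cell-level regression on the same terms with 11 residual df, weighted if site volumes differ.

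**Section 6.2.** Add site and period terms and a site-by-period frailty.

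**Both.** Do not rely on an uncorrected site-level sandwich variance with four sites.

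**Section 2.1.** State an assumed range of ICC and CAC, and recompute power under the new model.

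**Cost.** The change is SAP wording and a different model call, but precision falls. Even with no site-by-period variation, the log-OR half-width goes from 1.96 x 0.102 = 0.20 to 2.20 x 0.187 = 0.41, about double. The t reference accounts for only 2.20/1.96 = 1.12, or 12%; the rest is the price of adjusting for site and period in this design.

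Power was simulated for one such corrected analysis: site and period terms, a site-period overdispersion factor never below 1, and t on 11 df. The settings were latent-scale ICC 0 to 0.10, with CAC 0.5 or 0.8 where the ICC was above 0. Power for 25% v 50% was at least 92% throughout. For 25% v 31% it was about 14-24%, against the 80% stated for a 6-point increase. This method is somewhat conservative (type I error 1.6-4.6%), but the uncorrected site + period model reaches only about 38% with no clustering at all. The 80% statement therefore needs restating.

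### The primary model of this stepped-wedge trial omits period and site, so the deciding odds ratio is confounded with calendar time and exposed to site differences

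*SAP*

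**What the plan says.** Section 2 describes the design: "This study is a prospective, stepped-wedge cluster randomized trial", randomized by site. "There will be five, 10-week study periods and four sites". The schedule is: "In the first period, no sites will receive the intervention. During each subsequent period, one site will crossover to receive the intervention".

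Section 6 sets the primary model: "The primary analysis will include an effect for intervention, and subsequent sensitivity analyses will include fixed effects for time and site". The stated purpose of those sensitivity analyses is to test for heterogeneity of effect. The trial is decided by whether the 95% confidence interval of the odds ratio excludes 1.0. Up to five covariates may be added if they are imbalanced between arms. The candidates are patient characteristics, provider type, arrival modality, triage level and social determinants of health; neither period nor site is among them.

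The sample size section on the multivariable models confirms that the demotion is intended: "the model for sensitivity analyses will have up to 9 degrees of freedom", made up of the intercept, three site terms, four period terms and one treatment term.

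Section 6.2 treats time to antibiotics in the same way: "Analysis will use a Cox proportional hazard model with a fixed binary effect for treatment".

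**The concern.** The crossover schedule ties exposure to calendar time. Period 1 is all control, period 5 is all intervention, and the share of exposed sites rises in between. Randomizing the order in which sites cross cannot break this link, because every order gives the same rising share. Any improvement or decline in sepsis care, seasonal change or shift in case mix over the 50 weeks is credited to the tool unless period is in the model.

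Site works differently. Because the order is randomized, site bias averages zero over all orders. In the one order that is drawn, however, the first site contributes intervention data for four of five periods and the last for one of five. With four sites there is little chance of balance. The intervention-only model also treats encounters from the same site as independent, so its standard error ignores between-site variation.

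At stake is the confidence interval on which the primary conclusion rests. It would not have its nominal error rate, and a modest trend or site difference could create or hide a significant result.

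**Working it through.** **Inputs from the SAP.** Four sites, five periods and one crossover per period from period 2 (section 2); N = 2054, 25% control rate, 50% intervention rate and a claimed 80% power for a 6-point increase (section 2.1); two-sided 5% level (section 6).

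**Assumptions.** Equal cells of 2054/20 = 102.7 patients. Ten of the 20 site-periods are on the intervention, so there are 1027 patients per condition. Drift and site spread are illustrative, because the SAP gives neither.

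**The plan's own figures.** An unclustered two-proportion test with 1027 per arm gives more than 99.9% power for 25% versus 50%, and an increase of 5.5 points detectable with 80% power. Power at exactly 6 points is 85.8%. Both agree with the stated figures (above 90%; 6 points after rounding). They contain no site or period term.

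**How exposure lines up with time and site.**
- Exposed share by period: 0, 0.25, 0.50, 0.75, 1.00.
- Exposed share by site, in crossover order: 0.80, 0.60, 0.40, 0.20.
- Mean period is 4.0 for intervention cells and 2.0 for control cells. The correlation of intervention with period is 0.71.

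**Bias from a trend, no true effect.** With a drift of d points per period, the expected difference between conditions is d × (4.0 − 2.0) = 2d. The type I error is Φ(z − 1.96) + Φ(−z − 1.96), where z = log OR / SE and SE² = 1/[1027·p₁(1 − p₁)] + 1/[1027·p₀(1 − p₀)].

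| Drift per period | Control p₀ | Intervention p₁ | Spurious OR | z | Type I error |
|---|---|---|---|---|---|
| +1 point | 0.26 | 0.28 | 1.11 | 1.02 | 17.5% |
| +2 points | 0.27 | 0.31 | 1.21 | 2.00 | 51% |
| +3 points | 0.28 | 0.34 | 1.32 | 2.94 | 84% |

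The bias in the last row equals the 6 points that section 2.1 says can be detected.

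**Site differences, no trend, no true effect.** With site baselines of 15, 22, 28 and 35%, the type I error averages 44% over all 24 crossover orders, with a range of 5% to 93%. With an even spread from 20% to 30%, it averages 17%, and the worst order gives 41%.

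**Model with site and period.** In simulations of binomial data with about 103 patients per cell, under common drifts or constant site differences, this model kept the type I error between 4.3% and 5.7%.

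**Cost in precision.** The variance of the intervention indicator is 0.5 × 0.5 = 0.25. The variance of its period means is 0.125 and of its site means 0.05. Period and site together explain (0.125 + 0.05)/0.25 = 70%. The variance inflation is 1/(1 − 0.70) = 3.33, so the standard error is √3.33 = 1.8 times larger. From the logistic information matrix on the 4 × 5 grid:

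| | Intervention only | With site and period |
|---|---|---|
| Power, 25% vs 50% | >99.9% | >99.9% |
| Power, 25% vs 31% | 85.6% | 38.1% |
| Increase detectable, 80% power | 5.5 points | about 10.4 points |

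**The case against.** **The adjusted model is prespecified, so readers will see it.** True, but the SAP does not tie its significance rule to that model or say what follows if the two disagree. Main effects of time and site also do not test heterogeneity of effect, which is the reason given for fitting them; that would need interactions.

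**The magnitudes are hypothetical.** This stands as a limit on size. The SAP supports no particular trend or spread, and a drift of 3 points per period means 12 points from period 1 to period 5. With neither drift nor site differences, the intervention-only model holds 5%. If the true effect were the planned 25 points, a bias of 2 to 6 points would be unlikely to reverse the verdict, though it would distort the estimate. The link between exposure and calendar time needs no assumption.

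**The replacement is not a complete cure.** This also stands. A fixed-effects model still treats encounters within a site-period as independent. With random site-by-period variation (an assumption) of SD 2, 3 or 5 points and no true effect, its simulated type I error is about 8%, 11% and 20%. The intervention-only model does about as badly (7%, 9% and 21%). Adjustment gives no protection against this source, but it removes common trends and constant site differences, which the current primary model does not.

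**The protocol might handle it.** The SAP states the primary model outright, so this is a choice made in the SAP and not a detail left to another document.

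**Conclusion.** The concern holds, and the primary model must be changed. Confounding with calendar time is built into the design and needs no assumption. Exposure to site differences depends on the order drawn, and four sites offer little prospect of balance. Nothing elsewhere in the SAP corrects either, and the Cox model for time to antibiotics has the same fault.

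The consequence ranges from none, if care is stable and sites are alike, to a false-positive rate well above 50% under a drift of a few points per period. The validity of the primary test therefore rests on conditions that the SAP neither states nor supports. The figures assume equal cells and no within-site correlation beyond fixed site and period effects.

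**What to change.** - **Section 6:** make the primary analysis a logistic model with intervention, site (3 df) and period (4 df), which is the nine-parameter model already sized in the SAP. Keep the intervention-only model as descriptive or supportive. Attach the confidence-interval rule to the adjusted model, and use the same terms for the other binary outcomes. If heterogeneity of effect is of interest, name the interaction terms.
- **Section 6.2:** fit the Cox model with intervention and period, stratified by or adjusted for site.
- **Section 2.1:** restate the increase detectable with 80% power at about 10 points, and recompute the detectable difference for time to antibiotics under the same model.
- **Limitation to record:** residual site-by-period correlation with only four clusters is not resolved by these terms. The SAP should say how it will be examined.

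The cost is wording and a recalculation; no new data are needed. The sample is large enough for the model: by the SAP's own rule it needs 90 outcomes, or 360 patients, against 2054 expected. The real price is precision. The standard error is about 1.8 times larger, and power for a 6-point increase falls from about 86% to 38%, while the planned 25% versus 50% comparison keeps more than 99.9%.
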